3.3 Premature withdrawal from a study for a single patient

If at any time the constraints of this protocol are considered to be detrimental to the patient's health and/or the patient no longer wishes to continue protocol therapy, the participant will be withdrawn from the study and the reason(s) for withdrawal documented in the case report forms.

Any participant will be withdrawn from the study in the following scenarios:

- Death
- Anaphylaxis
- Allergic reaction with urticarial, rash or dyspnea,
- Cardiac arrest
- Atrial or ventricular fibrillation
- Ventricular Tachycardia
- Syncope
- AV block (2nd degree type II or 3rd degree)
- New QTc prolongation >60ms greater than baseline or >470ms for men or >480ms for women
- Troponin elevation > 0.03 ng/mL
- Sustained increase or decrease in SBP of >30 mmHg systolic or >20 mmHg diastolic
- Sustained vital sign abnormalities
 - HR<40 or >120 beats per minute
 - SpO₂ <92%
 - Temperature <36 C or >38°C
- ALT/AST \geq 3xULN AND total bilirubin \geq 2xULN
- AST/ALT \geq 8xULN
- Thrombocytopenia
- Clinically meaningful CBC abnormalities (compared to baseline)
- Altered mental status (delirium, inability to follow simple commands)
- Seizures
- Persistent visual disturbances
- General or specific changes in the patient's condition that render the patient unable to receive further treatment in the judgment of the investigator
- Suspected or confirmed pregnancy
- Serious non-compliance with the study protocol
- Lost to follow-up
- Patient withdraws consent
- Investigator removes the patient from study
- Investigator decides to close the study

If a participant withdraws from the study, the participant will be replaced in order to provide the required number of evaluable subjects. Subjects will be withdrawn if the investigator decides that discontinuation is in the best interest of the subject, or the subject requests withdrawal from the study.

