2.3.1 Subject Selection

Patients with neuropathic pain meeting inclusion criteria will be recruited from the Saint Louis community until 28 participants have completed both study sessions.

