2.4.5 Observations and Measurements

2.4.5.1 Primary Outcome Measures

Primary outcome:

The primary objectives are to evaluate the pharmacokinetics and the tolerability of ondansetron and tarividar single dose iv co-administration (in comparison to ondansetron administration alone) in patients with neuropathic pain.

Pharmacokinetics:

-Venous blood sampling for pharmacokinetics will be obtained: at 0, 15, 30, 60, 90, 120, 180, and 240 minutes from the beginning of ondansetron infusion.

-A CSF sample will be obtained via lumbar puncture between 30 and 180 minutes from the beginning of ondansetron infusion, for the assessment of ondansetron concentration in the CSF using population PK approach.

-CSF to plasma ratio of ondansetron will be calculated, and compared between the two study arms

Tolerability:

-Spontaneous reporting of adverse effects

- Vital signs (pulse oximetry, blood pressure): before infusion and 30, 60, 120, 180 and 240 minutes after end of ondansetron infusion.
- 12-lead ECG: At baseline and prior to discharge after each treatment session.
- Troponin T: at screening and prior to discharge after each treatment session.
- Blood chemistry (CMP) and count (CBC) at baseline and at 3-week time point after each treatment session.
- In patients who are concomitantly treated with SSRI or SNRI medications that are allowed for inclusion (duloxetine ≤60mg/day, citalopram ≤20mg/day, or Escitalopram ≤10mg/day, additional assessments will be performed at the time of vital sign assessments (baseline and 30, 60, 120, 180 and 240 minutes after end of ondansetron infusion) to evaluate confusion, restlessness, dilated pupils, muscle twitching or rigidity, and sweating. This will be performed to identify signs suggestive of serotonin syndrome.

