2.4.7 Statistical Methods

All demographic, sensory, analytical and patient-reported data will be captured on case report forms, manually entered to a Research Electronic Data Capture (REDCap) database that will be created for the project, and will be verified by an independent study team member. Plasma and CSF concentrations of ondansetron will be analyzed using a previously validated liquid chromatography method.³⁹ Non-compartmental PK analysis will be performed to construct the concentration-time curves of ondansetron in human plasma with and without tariquidar.³¹ Ondansetron concentration in CSF will be used to evaluate biodistribution of ondansetron to CNS, by the means of CSF to plasma concentration ratio. We do not expect missing outcomes data as all primary and most secondary outcomes will be collected with the participants physically present with the research team. Any missing data will be described, but no data imputation will be attempted. Intergroup comparisons for parametric data will be performed by paired t-test, and for non-parametric data by Wilcoxon signed-rank test for paired samples. McNemar's test will be used to compare paired nominal data, and Fisher's exact test to compare non-paired nominal data.

Sample size:

Change in spontaneous pain reduction (secondary outcome) was used to determine the sample size for the study. The baseline pain intensity (\pm SD) of patients with peripheral neuropathy we have recruited to various studies over the past two years have been 6.3 ± 2.1 . This proof of concept study expects to demonstrate a 30% difference in pain reduction between the two intervention sessions. Given that in a published study of IV ondansetron in NeuP a 20% pain reduction has been observed (although not different from placebo), we assume pain intensity of 5.1 ± 2.1 in ondansetron+placebo group, and expect pain intensity of 4.0 ± 2.1 in ondansetron+tariquidar group at the 60-120 minute timeframe. To determine a significant difference with two-tailed $\alpha < 0.05$ and 85% power (effect size 0.52), 28 subjects will be required in this cross-over study. We expect to enroll 28-32 participants to the study to reach 28 evaluable participants.

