3.0 Management of Intercurrent Events

3.1 Adverse Experiences

The investigators will closely monitor subjects for evidence of systemic adverse events. All adverse events will be reported and followed until satisfactory resolution. The description of the adverse experience will include the time of onset, duration, severity, etiology, relationship to the study drug (none, unlikely, possible, probable, highly probable), and any treatment required. Participants will notify the monitoring physician/RN coordinator of any adverse experience during the study period.

At discharge, subjects will be provided with contact information for team members and instructed to call if any adverse events occur.

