3.2 Dose Limiting Toxicities

The dose-limiting toxicities (DLT) for the study are defined as follows:

- New QTc prolongation >60ms greater than baseline, or QTc>450ms
- Troponin T elevation > 0.03 ng/mL
- Syncope
- Sustained increase or decrease in SBP of >30 mmHg systolic or >20 mmHg diastolic
- Sustained vital sign abnormalities
 - HR<40 or >120 beats per minute
 - SpO2 <92%

- ALT/AST \geq 3xULN AND total bilirubin \geq 2xULN
- AST/ALT \geq 8xULN
- Altered mental status (delirium, inability to follow simple commands)
- Persistent visual disturbances

If DLT is observed in >2 participants, ondansetron dose will be reduced to 12 mg for all new participants.

If further DLT is observed in >2 participants receiving 12 mg ondansetron, the dose will be reduced to 8 mg for all new participants.

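### Does the primary tolerability comparison lose the participants who are withdrawn and replaced after their first session?

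*Combined protocol and SAP*

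**What the plan says.** Section 2.4.5.1 makes this a comparative primary objective: "tolerability of ondansetron and tarividar single dose iv co-administration (in comparison to ondansetron administration alone"). Under it the section lists measurements: adverse effects, vital signs, ECG, troponin, blood chemistry and counts, and signs of serotonin syndrome. It defines no summary endpoint and no analysis set.

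Section 2.4.7 assigns tests by type of data. For continuous data they are the paired t-test or the Wilcoxon signed-rank test. McNemar's "test will be used to compare paired nominal data", and Fisher's "exact test to compare non-paired nominal data". None is tied to tolerability by name. On missing values the section says: "Any missing data will be described, but no data imputation will be attempted".

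Recruitment continues "until 28 participants have completed both study sessions" (section 2.3.1), and section 3.3 sets the replacement rule: "If a participant withdraws from the study, the participant will be replaced in order to provide the required number of evaluable subjects".

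Section 3.1 states: "All adverse events will be reported and followed until satisfactory resolution". Section 3.3 requires withdrawal reasons to be documented in the case report forms. Section 3.2 lowers the ondansetron dose for new participants when more than 2 have a dose-limiting toxicity (DLT). Section 3.4 sets a stopping criterion at more than 7 participants meeting the withdrawal criteria because of adverse effects.

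**The concern.** In a crossover analysed by pairs, a participant withdrawn after session 1 has no second value and contributes nothing. Here withdrawal is not random: section 3.3 makes it mandatory after a long list of adverse events. Those events are the ones that a tolerability comparison most needs, and each such participant is then replaced by someone else. The only population that the plan counts is people who completed both sessions, and most of the named tests are paired.

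If the analysis followed those cues, the rates and the risk difference for serious intolerance would be understated on both treatments. The synopsis hypothesises that the combination will be tolerable, and section 2.2 says that tolerability should be known before large efficacy studies. A halved rate would therefore bear on the main message.

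**Working it through.** **Is there a figure in the plan to reproduce?** Not for tolerability. The target of 28 comes from pain, a secondary outcome, with effect size (5.1 − 4.0)/2.1 = 0.52 (section 2.4.7). It says nothing about which participants enter the tolerability tables.

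**Do DLTs force withdrawal?** Comparing the list in 3.2 with the list in 3.3, every DLT is also a withdrawal criterion, with one exception. The DLT list has "New QTc prolongation >60ms greater than baseline, or QTc>450ms". Section 3.3 repeats the 60 ms rise but uses absolute limits of 470 ms for men and 480 ms for women. Section 2.4.3 withdraws a participant whose QTc exceeds 450 ms at the ECG before the second infusion, and section 3.6.1 treats values between 450 and 500 ms as mild. These passages must be reconciled with each other. That is a separate matter from the analysis set.

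**What would a completer-only comparison lose?** Let pT and pP be the risks per session of a withdrawal-level event on tariquidar and placebo. The documents give neither, so the values below are assumptions. Further assumptions are equal allocation to the two orders, no period effect, independent sessions, every session-1 event leading to withdrawal, and session-2 events kept among the completers.

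- Completer rate on tariquidar: pT(1 − pP)/(2 − pT − pP)
- Completer rate on placebo: pP(1 − pT)/(2 − pT − pP)
- Share of tariquidar events omitted: 1/(2 − pP); of placebo events: 1/(2 − pT)
- Expected enrolment for 28 completers: 56/(2 − pT − pP)

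| Assumed pT v pP | Completer rates | True difference (points) | Completer difference (points) | Omitted, tariquidar / placebo | Enrolled |
|---|---|---|---|---|---|
| 5% v 1% | 2.55% v 0.49% | 4.0 | 2.1 | 50.3% / 51.3% | 28.9 |
| 10% v 2% | 5.21% v 0.96% | 8.0 | 4.3 | 50.5% / 52.6% | 29.8 |
| 20% v 5% | 10.86% v 2.29% | 15.0 | 8.6 | 51.3% / 55.6% | 32.0 |

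For the last row, tariquidar is 0.20 × 0.95/1.75 = 10.86% and placebo is 0.05 × 0.80/1.75 = 2.29%. In counts, the tariquidar events lost are about 0.7, 1.5 and 3.2 in the three rows.

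The last row is hard to square with a trial that finishes as planned. In simulation under these rates, more than 2 participants have an event in about 98% of runs, and the more-than-7 rule stops about 50%. For the first row the figures are about 25% and 0%.

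**Does any section require that analysis?** No. The target of 28 governs recruitment and replacement. Sections 3.1 to 3.4 report, record or count these events with no completer restriction. Section 2.4.7 says that missing data will be described, and it provides Fisher's test for unpaired nominal data. Milder session-1 events, and the vital signs, ECG and laboratory values of participants who continue, stay paired in any case.

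**What would a prespecified session-1 test add?** The upper end of planned enrolment, 32, gives 16 per group. Fisher's exact test then needs 5 events against none to reach p = 0.043; 4 against none gives p = 0.10. Its power in the three rows is about 0.1%, 1.2% and 9.9%.

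**The case for a change.** The best case for a change is that the cues point one way. The only counted population is completers, the between-session tests for a crossover are paired, and section 2.4.7 expects no missing outcomes although section 3.3 creates missing second sessions exactly when the first is badly tolerated. Enrolment of 28 to 32 already foresees up to four participants with no stated place in the primary comparison. A sentence defining the set would cost little.

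Part of this stands. The set is not written down, and the arithmetic of a completer-only comparison is right. At 20% v 5%, exact McNemar rejects in 3.5% of simulated trials among completers, against 26.9% if each session-1 withdrawal is counted as a discordant pair. That second figure takes the missing session as event-free. As an example of estimates, 3 of 28 completers is 10.7% (exact 95% CI 2.3% to 28.2%), while 6 of 31 treated is 19.4% (7.5% to 37.5%).

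What does not stand is the step from an unstated set to a biased result. The claim that the combination is tolerable rests on an absolute rate, which needs no pairs and can be computed from records that the protocol requires. Nor is it accurate that no test is available: tests are given by data type, including one for unpaired data. The loss also falls on both treatments, so the main effect is attenuation and not a reversal. The ratio moves from 4.0 to 4.75 in the highest scenario.

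**Conclusion.** No change follows. The plan leaves out a detail that a trial statistician would ordinarily fill by summarising tolerability in all treated participants, by the treatment received in each session. All the data for that are collected, and nothing in the protocol stands against it.

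The feared loss, about half of withdrawal-level events, arises only if someone chooses a completer-only comparison. Its absolute size depends on event risks that the documents do not give: about 0.7 of a tariquidar event at 5% v 1%, and 3.2 at 20% v 5%, a level at which the trial's own dose-reduction and stopping rules would probably intervene. The limited prior data point to few events: no troponin rise in 8 participants (section 2.2), and no arrhythmia or other serious side effect in 15 given 16 mg ondansetron (section 3.5.4). Both series are small.

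With so few events expected, tolerability will be judged from listed events and rates with intervals. Prespecifying a further test would rarely alter that reading.

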3.4 Adverse experiences and premature termination of the study

If any patient should suffer any serious adverse effect, including but not limited to serious neurologic or cardiovascular dysfunction or a reaction concerning for anaphylactic or anaphylactoid reaction, patient recruitment and randomization will be halted until the etiology of such an adverse reaction can be determined.

If two or more participants suffer any serious adverse effect, the study team will discuss premature termination of the study with Washington University IRB and the FDA.

If more than 7 participants meet the early withdrawal criteria, due to serious or non-serious adverse effects, the study will meet the early stopping criteria.

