2.4 Design and Procedures

2.4.1 Study Design

Randomization and Blinding: The study is designed as a prospective, randomized, double-blind, cross-over experiment in patients with neuropathic pain. After signing informed consent and meeting eligibility criteria, participants will receive two 16 mg IV infusions of ondansetron, approximately 3 weeks apart. Participants will be randomized to the order of tariquidar (4mg/kg dose in 500mL D5W) and placebo (D5W solution) co-administration with ondansetron.

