2.4.3 Study Period

Participants will be studied in the Washington University Pain Center, or in the Clinical Research Unit (CRU) of Washington University School of Medicine, with continued presence of research and nursing personnel. The study will comprise three sessions over an approximately 28-day period (Figure 2A). As previously described, the screening visit will take place within about 7 days prior to the first study visit. The screening visit can be coordinated on the same morning as test day 1.

Intervention:

Each participant will receive two IV infusions of ondansetron, 3 weeks apart, in randomized order. Placebo (D5W) or tariquidar (4mg/kg dose in D5W) will be administered IV over 60 minutes according to randomization schedule. Ondansetron will be diluted in 100mL D5W, and tariquidar will be diluted in 500mL D5W. Starting 30 minutes after the initiation of tariquidar/placebo, a 15-min ondansetron co-infusion will be given, to time its peak brain concentration with potent Pgp inhibition (Figure 3). A 3 weeks interval between the two sessions (> 5 half-lives) will allow the elimination of the first dose of ondansetron and tariquidar. A 12-lead ECG will be repeated prior to the second infusion to confirm that subjects still have a normal QTc and sinus rhythm. Any subject who has a QTc>450ms will not receive the second ondansetron dose and will be withdrawn from the study. A blood sample will be drawn at the 240 min time point for troponin levels. If troponin levels are elevated, the patient will be immediately evaluated by a physician and a cardiology consult will be obtained. Further assessment and treatment of these subjects is described below in section 3, "Management of Intercurrent Events".

Vital signs (pulse oximetry and 3-lead ECG; non-invasive blood pressure) will be monitored before infusion and approximately 30, 60, 120, 180 and 240 minutes after end of ondansetron infusion. A 12-lead ECG will be performed at baseline and before the participants are discharged.

Adverse effects will be collected by spontaneous participant reporting, but also asked about every 30 minutes.

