3.5.4 Potential risks from ondansetron

Ondansetron is a widely-used drug approved for prevention of chemotherapy-induced, radiotherapy-induced, and postoperative nausea and vomiting. It is commonly used off-label for treatment of nausea and vomiting. The most common reported side effects (~10%) include headache, constipation, and fatigue. Less common (<10%) include drowsiness, diarrhea, fever, anxiety, transient liver enzyme increases, or burning at

injection site. Rare side effects (<1%) include cardiac arrhythmias, ECG changes, dry mouth, anaphylaxis, transient blindness, and hypokalemia.

The FDA has issued a drug safety communication regarding the risk of QTc prolongation and potential progression to torsades de pointes. The risk of cardiac side effects was determined to be dose-dependent with a maximum QTc prolongation by 20msec after 32mg IV administration; consequently, 32mg IV doses are no longer approved. 16mg IV infusion doses (as proposed in this study) are still approved and frequently used for chemotherapy-induced nausea and vomiting. Risk of arrhythmia is increased by comorbidities including: congenital long QT syndrome, congestive heart failure, bradycardias, or patients taking concomitant medications that prolong the QT interval. All such patients would be excluded by our proposed exclusion criteria. Additionally, in our recent study, none of the 15 subjects who received 16mg intravenous ondansetron (meeting the same inclusion/exclusion criteria as in this study), experienced arrhythmias or any other serious side effects (NCT02901054).

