3.6 Procedures to Minimize Potential Risks

Drug infusions will be administered in the Washington University Clinical Research Unit under the supervision of the PI and the co-investigators. Subjects will be monitored by study personnel during infusions, and dedicated RN personnel is available 24-hours a day on site.

Inclusion and exclusion criteria, monitoring, and the clinical protocol are designed to ensure that risks are absolutely minimal. Participants are informed that participation is voluntary and they may refuse to participate and may withdraw from the study at any time without penalty. A pregnancy test will be performed on women of childbearing potential and subjects excluded if pregnant. Subjects will be told that in the event of a physical injury as the direct result of study procedures, they will be cared for by a member of the investigating team at no cost, within the limits of the Washington University compensation plan.

Subjects will be instructed at the beginning of the visit that they can alert the investigator any time they experience bothersome side effects. In particular, they will be instructed to immediately report palpitations or dizziness/lightheadedness. Continuous physiologic monitoring (ECG, pulse oximetry, and intermittent non-invasive blood pressure) will be used from the beginning of drug infusion until 2 hours after ondansetron infusion is complete. Medical personnel will be immediately available throughout the visit. The subject can voluntarily withdraw from the study at any time.

With regard to confidentiality; 1) all subjects will be assigned a study ID number, 2) Samples will be kept

confidentially. They will be coded, with a key to the code linking code numbers to names kept at a separate location, under lock and key. 3) The link to identifiers will be destroyed at the end of the study. 4) Data will be stored under lock and key (office, file cabinet) and only the investigators and research team will have access. If data are published, there will be no link to identifiers. Study data will not be revealed to any organization, individuals other than the subjects, or the subjects themselves. 5) Study data will not be entered in subjects' medical records.

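### The serious-event pause in section 3.4 stops recruitment and randomization but does not require holding the second infusion of participants already randomized

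*Combined protocol and SAP*

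**What the plan says.** Section 3.4 sets a mandatory response to one serious adverse effect in any patient: "patient recruitment and randomization will be halted until the etiology of such an adverse reaction can be determined". The rule does not mention infusions or participants already in the study. Two or more such events lead to a discussion of termination with the IRB and the FDA. More than 7 participants meeting the early withdrawal criteria meets the stopping criteria.

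On the design, section 2.4.1 states: "Participants will be randomized to the order of tariquidar" and placebo. Section 2.4.3 adds: "Each participant will receive two IV infusions of ondansetron, 3 weeks apart, in randomized order". One act of randomization therefore covers both infusions.

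Other provisions that bear on a second infusion:

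- **Section 2.4.3:** "A 12-lead ECG will be repeated prior to the second infusion to confirm that subjects still have a normal QTc and sinus rhythm". A QTc above 450 ms means no second dose and withdrawal.
- **Section 3.2:** after dose-limiting toxicity in more than 2 participants, "ondansetron dose will be reduced to 12 mg for all new participants".
- **Section 3.3:** withdrawal follows listed events in that participant, or judgment: "Subjects will be withdrawn if the investigator decides that discontinuation is in the best interest of the subject". The investigator may also close the study.
- **Section 3.6:** infusions are given "under the supervision of the PI and the co-investigators".
- **Section 3.7:** adverse events are reported to the HRPO, and the DSMB reviews every serious adverse event report.

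**The concern.** The pause lasts until the cause is known, so its evident purpose is to prevent further exposure to an unexplained hazard. In a single-dose parallel trial, stopping randomization would achieve that. In this crossover it does not, because participants between sessions have been recruited and randomized and still have an infusion to come. They are among the people closest to their next exposure, and for them the hold rests on case-by-case judgment, while new entrants get a firm rule.

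The hazard is not well characterized. Section 2.2 says that tolerability of the combination in patients with neuropathic pain is unknown. The cardiovascular safety data it reports come from 8 participants, only 2 of them at 16 mg ondansetron.

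**Working it through.** **1. Does any provision require a hold on other participants' second infusions?**

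| Provision | What it does | Requires a hold? |
|---|---|---|
| 3.4, one serious event | Halts recruitment and randomization | No |
| 3.4, two or more | Discussion with IRB and FDA | No |
| 3.4, more than 7 meeting withdrawal criteria | Stopping criteria met | Only at that count |
| 2.4.3, ECG before second infusion | Checks that participant's own QTc and rhythm | No; it would not detect an anaphylactoid or neurologic hazard seen in someone else |
| 3.2, dose reduction | Needs more than 2 participants with toxicity; applies to new participants | No |
| 3.3, withdrawal | The individual's own events, or investigator judgment | No; permits it |
| 3.6, supervision | Investigators oversee infusions | No; permits it |
| 3.7, DSMB and HRPO | Reporting and review | No suspension stated |

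**2. How many second infusions would fall due in a pause?**

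The plan gives no figure to reproduce. Inputs: N = 28 to 32 enrolled (section 2.4.7), enrollment of about 24 months = 730 days (synopsis), 3-week interval (section 2.4.3). Assumptions: even accrual, Poisson counts, and 1:1 allocation of order (the ratio is not stated).

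For a pause of d days, d up to 21:

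- Expected number m = N × d / 730; for example 28 × 7 / 730 = 0.268 and 32 × 21 / 730 = 0.921.
- P(at least one) = 1 − exp(−m).
- For infusions containing tariquidar, replace m by m/2.

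| Pause | m, all | P(≥1), all | m, tariquidar | P(≥1), tariquidar |
|---|---|---|---|---|
| 7 days | 0.268-0.307 | 0.235-0.264 | 0.134-0.153 | 0.126-0.142 |
| 14 days | 0.537-0.614 | 0.415-0.459 | 0.268-0.307 | 0.235-0.264 |
| 21 days | 0.805-0.921 | 0.553-0.602 | 0.403-0.460 | 0.332-0.369 |

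The 21-day row also equals the mean number of participants between sessions at any time. If accrual took 12 months instead (an assumption), that mean would be 28 × 21 / 365 = 1.6 to 32 × 21 / 365 = 1.8, and P(≥1) would be 80-84%.

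**3. How likely is a pause?**

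The documents give no serious-event rate for the combination in patients. Section 3.5.4 reports that "none of the 15 subjects who received 16mg intravenous ondansetron" had an arrhythmia or other serious side effect. The one-sided 95% upper bound for 0 of 15 is 1 − 0.05^(1/15) = 0.181, so those data cannot exclude rates up to 18%, and they concern ondansetron alone. I assume p = 1% to 5% per participant.

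P(at least one serious event) = 1 − (1 − p)^N:

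- p = 0.01: 0.245 (N = 28), 0.275 (N = 32)
- p = 0.05: 0.762 (N = 28), 0.806 (N = 32)

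**4. Overall chance that a second infusion falls due in the first pause**

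This is the product of steps 2 and 3. The low end uses p = 0.01 and N = 28; the high end uses p = 0.05 and N = 32.

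| Pause | All second infusions | Containing tariquidar |
|---|---|---|
| 7 days | 0.245 × 0.235 = 0.058 to 0.806 × 0.264 = 0.213 | 0.031 to 0.115 |
| 21 days | 0.245 × 0.553 = 0.136 to 0.806 × 0.602 = 0.485 | 0.081 to 0.297 |

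**The case against.** The strongest reply is that this is a gap in wording and not an instruction to dose. The protocol never says infusions continue during a pause. The investigators supervise every infusion, may withdraw anyone in that person's interest, and may close the study. With fewer than one participant between sessions on average, judgment is workable. This stands as far as it goes: the finding is only that a hold is not required. It does not explain why new entrants get a mandatory halt and participants already randomized do not.

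Some limits on the numbers also stand:

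- They count infusions falling due in a pause. They become exposures only if the investigator proceeds each time, so they are ceilings.
- The 1-5% event risk is assumed. The human data cited are reassuring though small: no troponin rise and no significant QTc difference in the 8 participants of section 2.2, and no serious events in the healthy-volunteer study of 4-8 mg/kg tariquidar in section 3.5.5.
- If the hazard comes from tariquidar, the tariquidar-only figures are the relevant ones. The other half of second infusions are 16 mg ondansetron with placebo, an approved dose.
- The institutional monitoring plan and guidelines cited in section 3.7 are not in the documents and could contain a hold rule.

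It can also be said that a wider halt is too broad, since a serious lumbar puncture complication would freeze all dosing, with no time limit. Both features already belong to the existing 3.4 trigger, and identifying the puncture as the cause would end the pause. Replacement of a withdrawn participant must wait until recruitment resumes, but it is not lost.

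**Conclusion.** The concern holds. Followed literally, section 3.4 does not reach a pending second infusion, and nothing else in the documents requires one to be held. The textual point depends on no numerical assumption.

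The scale is modest: fewer than one second infusion per pause on average, with a 24-26% chance of at least one in a 7-day pause and 55-60% in a 21-day pause, given even accrual over 24 months. Over the whole trial, with an assumed 1-5% event risk, the ceiling is 6-21% and 14-49% respectively, or 3-12% and 8-30% for infusions containing tariquidar if order is allocated 1:1. Because it concerns participant safety and is simple to correct, it should be changed. Confidence is high in the reading of the text and lower in the overall probabilities.

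**What to change.** Amend the first rule in section 3.4 so that the halt covers recruitment, randomization and all study-drug infusions, including pending sessions in participants already randomized. Add one sentence: a second session delayed by the pause may be given once it is lifted, after the pre-session checks already required.

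The cost is one phrase, one sentence and an occasional delayed or unpaired session, on average 0.27-0.92 per pause for pauses of 7 to 21 days. A delay only lengthens a washout that section 2.4.3 already treats as sufficient at 3 weeks, and section 2.4.1 already makes the interval approximate. A participant who withdraws because of the delay is replaced under section 3.3 once recruitment reopens. No endpoint, sample size or analysis changes.
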